8.2.2 Cell proliferation (Ki-67 labeling index)

A common endpoint of pathways affected by sulforaphane is cell proliferation. Ki-67 labeling is a validated indicator of proliferative index and can be readily detected in bronchial biopsy material (75-77). Ki-67 labeling index (Ki-67 LI) is positively associated with increased grade of bronchial dysplasia; a mean of 4% in normal and hyperplastic samples increased to 38% in biopsies with moderate or severe dysplasia (Table 4). When a serial set of matched biopsies were examined for change over time there was correlation between histological change and Ki-67 labeling scores. Ki-67 thus is an easily performed proliferative index that will be a primary endpoint in this study.

Table 4. Histology and Biomarkers in Bronchial Epithelium of High Risk Subjects

Study group	Histology	Ki-67 (mean %)
All subjects	Grade 1-2 (N=14 biopsies)	4%
	Grade 3-4 (N=16 biopsies)	20%

Grade 5-6 (N=39 biopsies)	38%
Serial Biopsies:	
No change (N=7)	Mean grade change 0
Progression (N=10)	Mean grade change +2
Improvement (N=4)	Mean grade change -2.5
	-17%
	+17%
	-21%

8.2.3 Apoptosis (TUNEL and Caspase-3)

Like the proliferative index, the apoptotic index will provide a measure of a final common pathway. Dietary SF significantly induced markers of apoptosis in lung tissue of mice after treated with tobacco carcinogens. Compared with control animals, mice given SF showed a statistically significant 6-fold increase (from 4.7 ± 1.9 to $29.3 \pm 4.7\%$) in activated caspase-3, and a 2-fold increase (from 12.7 ± 3.0 to $29.4 \pm 5.8\%$) in TUNEL (terminal transferase dUTP nick end labeling) of lung cells. Activated caspase-3 and TUNEL are representative markers for apoptosis (14). Thus we will perform TUNEL and caspase-3 assays on sections of bronchial mucosa from histologically normal and abnormal sites pre and post SF treatment.

8.2.4 Gene expression markers

Gene expression in the airway epithelium, which can be sampled by bronchoscopic and nasal brushings, represents an intermediate biological endpoint between underlying genetic or epigenetic alterations driving carcinogenesis and the clinical diagnosis of lung cancer. [name] (Co-I) and colleagues (19) recently validated that a 23-gene expression marker in epithelial cells collected from the normal-appearing main-stem bronchus significantly improved the diagnostic performance of bronchoscopy for detection of lung cancer. The combination of the 23-gene expression marker plus bronchoscopy had a sensitivity of 96% (95% CI, 93% to 98%) in the first cohort of patients and 98% (95% CI, 96% to 99%) in the second cohort of patients, independent of lesion size and location. In patients with a nondiagnostic bronchoscopic examination, the gene-expression classifier accurately identified cancer in 89%. The 23-gene expression marker is the first genomic classifier to improve the diagnostic performance of bronchoscopy for the detection of lung cancer. In the proposed study, we will evaluate if the SF treatment alters the gene expression of these 23 genes in the bronchial epithelium, and decreases the classifier score towards that seen with lung benign disease (78).

Using mRNA sequencing (mRNA-Seq), we profiled cytologically normal airway epithelial cells collected during auto-fluorescence bronchoscopy from high-risk smokers with (n=50) and without (n=25) bronchial premalignant lesions (PMLs). Using surrogate variable analysis, we identified 280 genes significantly differentially expressed between subjects with and without PMLs at false discovery rate (FDR)<0.002. The 280-gene signature has a significant concordant relationship to gene expression changes identified in PMLs adjacent to non-small cell lung cancer (NSCLC), in NSCLC tumors, and in the field of individuals with lung cancer (FDR<0.05). These data suggest that the change in certain gene expressions in bronchial epithelium takes place at premalignant stage. In the proposed study, we will

explore if the SF treatment alters the gene expression profile of these 280 PMLs-related genes in bronchial epithelium of the study participants.

The unified airway field of injury concept suggests that cigarette smoking renders injury throughout the entire respiratory tract. Studies have shown that tobacco-related gene expression alterations in the extra-thoracic epithelium of the nose and mouth similarly reflect the host response to cigarette smoke in the distal airway (79). Both nasal and bronchial epithelial cells demonstrate similar patterns of gene expression changes in response to cigarette smoking (73), suggesting that the nasal epithelium may be a surrogate biospecimen for monitoring the individual response to smoking and potentially the risk for lung cancer. More recently, we have demonstrated that the cancer-specific gene-expression changes in the bronchial epithelium are enriched among gene-expression alterations observed in the nasal epithelium from approximately 500 smokers with matched nasal and bronchial samples. These data suggest that genomic profiling of these relatively accessible airway cells may be an intermediate endpoint of chemoprevention for lung cancer. In the proposed study, we will explore whether SF-induced gene expression changes in bronchial epithelium mirror those in the nasal epithelium.

8.3 End of Treatment Evaluation

8.3.1 Histological Response

Histology on bronchial biopsies pre-treatment and post-treatment will be compared. All biopsies will be graded according to the WHO classification for bronchial epithelium (74):

WHO Classification	Grade
Normal	1.0
Reserve Cell Hyperplasia	2.0
Metaplasia	3.0
Mild Dysplasia	4.0
Moderate Dysplasia	5.0
Severe Dysplasia	6.0
Carcinoma in Situ	7.0
Carcinoma	8.0

Response will then be determined by three scoring methods:

- a) The worst histology grade per patient pre and post treatment.

Worse = \geq 1 point higher post treatment

Better = \geq 1 point lower post treatment

Same = same point score pre and post treatment

- b) Average histology (all biopsies scores/number of biopsies) pre and post treatment

Worse = \geq 1 point higher post treatment

Better = \geq 1 point lower post treatment

Same = same point score pre and post treatment

c) Dysplasia index (number of biopsies with dysplasia/total number of biopsies x 100) pre and post treatment.

Worse = $\geq 10\%$ higher post treatment

Better = $\geq 10\%$ lower post treatment

Same = $< 10\%$ difference post treatment

The final response determination will require the same response parameter (worse, better or the same) for 2 of the 3 methods.

8.3.2 Cellular Biomarker Response

A secondary endpoint is to determine if SF can modulate a proliferative intermediate marker Ki-67. Based on prior studies, a response will be considered as a decrease of > 10 in the labeling index, progression will be an increase of > 10 in the labeling index and no change will signify an increase or decrease of ≤ 10 .

We will also evaluate other biomarkers including apoptotic biomarkers TUNEL and caspase-3.

8.3.3 Gene Expression Response

The exact mechanisms for the observed SF-mediated 44 hemoprotection remain to be elucidated. The upregulation of NQO1 transcript suggests the activation of Nfr2 pathway (59). The alteration of lung cancer associated gene expression in BAL is an indication of SF's impact on lung cancer risk in the study population.

8.3.4 Safety and Toxicity Assessment

The safety and toxicity will be assessed by the study physician at the research clinic once every three months. We plan to closely monitor all study patients for potential SF-related adverse events. This includes both expected (based on previous clinical experience with oral SF) and unexpected events. The expected adverse events (AEs) are gastrointestinal including taste alteration (bad taste), dry mouth, belching, nausea, vomiting, and diarrhea. The frequencies of AEs were low and most were at moderate by grade (see Table 3).

9. STATISTICAL AND SAMPLE SIZE CONSIDERATIONS

This is a randomized, double blind, placebo-controlled study to evaluate the efficacy of SF as a chemopreventive agent. Eligible subjects are former smokers with ≥ 30 pack-years smoking history who quit smoking < 15 years, and are considered at high risk for developing lung cancer. The proposed duration of therapy will be 12 months for each subject. The primary objective of this trial is to assess whether oral SF supplementation elicits an increased histologic response when compared to placebo in this population over a 12-month treatment period. The planned sample size is 72 subjects (36 per treatment arm). A block randomization scheme will be used to ensure that both treatment and placebo group have the same proportion of men and women, respectively. The randomization will be done at the UPMC Hillman Cancer Center.

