5.2 Randomization

Eligible subjects will be randomly assigned to either Avmacol® or placebo arm with a 50%-50% chance. Each subject will be given three bottles of tablets at month 0 and at trimonthly clinical visits. Each bottle contains 250 tablets that will be sufficient for one month supply.

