9.1 Statistical Analysis for histological responses

Endobronchial histology scores will be first summarized within each bronchoscopy by using 3 separate endpoint measures pre and post treatment respectively: 1) dysplasia index (DI, number of biopsies with dysplasia/total number of biopsies x 100), 2) average of all histological scores (all biopsies scores/number of biopsies), and 3) worst biopsy score. The 3 summary end points will be analyzed within 4 different biopsy site groupings: all biopsies, biopsies from the 6 standard endobronchial sites only, site-matched biopsies from both bronchoscopies, and site-matched biopsies where the baseline biopsy is non-normal. For each patient, the mean of each of endpoints separately for each of biopsy site groupings pre and post treatment are then calculated. The primary endpoint is the dysplasia index (DI), which has a binomial distribution with at least 6 “trials” (i.e., 6 predetermined biopsy sites), and will be analyzed by generalized estimating equations (GEE) that constrains average baseline DI to be the same for both treatment and placebo groups, and tests whether average follow-up DI differs between the SF treatment and placebo groups. All other endpoints and biopsy site groupings are secondary endpoints. The primary analysis for the average and worst dysplasia scores will be a linear regression that assesses the difference in post-treatment scores by the two treatment groups, controlling for the same scores at pre-treatment. This analysis of covariance (ANCOVA) approach has optimal efficiency in a study design to assess the pre- and post-treatment measures with high within-subject correlation due to repeated measures (80). No interim analyses for futility or superiority will be performed, other than ongoing safety monitoring.

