Sample size consideration. In the iloprost trial, 57 former smokers were randomized to receive oral iloprost or placebo for 6 months. Treatment effects (adjusted for baseline levels) were statistically significant ($P \leq 0.01$) for all 3 endpoints (dysplasia index, average dysplasia score, worst dysplasia score). Anticipating a 20% dropout rate over 12 months, we will randomize at least 72 study subjects to ensure that 60 subjects complete our SF study. Assuming an average baseline dysplasia index of 22% and post-therapy 11% for subjects receiving SF, a simulation with 10,000 trials with a sample size of 60 subjects has yielded an 80% statistical power to detect a statistically significant (two-sided $p < 0.05$) treatment effect, using generalized linear models (binomial family, 6 biopsies) after controlling for baseline levels of DI. Calculations are similar for other endpoints, and actual power should be greater than the DI measure because they are continuous measures and have observed within-subject correlation (i.e., repeated measures).

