9.2 Statistical Analysis for Cellular Proliferation/Apoptosis Markers

Ki-67, caspase-3 and TUNEL will be quantified as % positive cells in two slides of each tissue block. First we calculate the average values of each of the 3 IHC markers over 6 tissue blocks within each bronchoscopy per patient separately for pre- and post-treatment. As described above for bronchial dysplasia measures, the primary analysis for these continuous measures will be a linear regression predicting post-treatment score by treatment group, controlling for pre-treatment score. We hypothesize that SF treated subjects will exhibit lower expression of Ki-67 and higher expression of caspase-3 and TUNEL relative to subjects in the placebo arm.

Sample Size Consideration. Using estimates of the mean and standard deviation (12.7 ± 8.2) of Ki-67 LI in the para-basal layer of bronchial epithelia of smokers (15) and the logit function, we back calculated plausible estimates of the mean (2.3676) and

variance (0.3480) of log-transformed baseline Ki-67 LI (81). Assuming these log-transformed Ki-67 LI values are normally distributed, we simulated 10,000 sets of data (n=60 each) and found an 84% statistical power with a two-sided $P<0.05$ to detect a treatment effect size of 37% for change in Ki-67 LI after 12 months of SF treatment (i.e., median Ki-67 LI of 10.7% at baseline and 6.7% at follow-up on SF). This detectable effect size is smaller than 61% reduction in cell proliferation marker in the SF treatment group (14). Furthermore, a recent randomized, double-blind, placebo-controlled phase 2 clinical trial involving 58 women found that oral intake of SF glucosinolate for 2-8 weeks resulted in a statistically significant reduction of mean Ki-67 LI ($P = 0.01$) (16).

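### Sex is balanced at randomisation but appears in none of the efficacy models; prespecifying it as a covariate is a cheap, modest improvement whose value depends on how prognostic sex is

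*Combined protocol and SAP*

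**What the plan says.** **Allocation.** Section 9 states: "A block randomization scheme will be used to ensure that both treatment and placebo group have the same proportion of men and women". The word stratified is not used, but blocking can deliver this only if it is done within sex. Section 5.2 says only: "Eligible subjects will be randomly assigned to either Avmacol® or placebo arm with a 50%-50% chance". The footnote to the section 6 calendar describes a single run of treatment numbers, issued in order of entry to stage 2, that determines the arm. Neither place mentions sex.

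**Analysis.** The primary DI analysis in section 9.1 uses "generalized estimating equations (GEE) that constrains average baseline DI to be the same for both treatment and placebo groups" and then compares follow-up DI between arms. For average and worst score, section 9.1 specifies a "linear regression that assesses the difference in post-treatment scores by the two treatment groups, controlling for the same scores at pre-treatment". For Ki-67, caspase-3 and TUNEL, section 9.2 specifies a "linear regression predicting post-treatment score by treatment group, controlling for pre-treatment score". The power simulation for DI controls for baseline DI alone. No section adds sex to an efficacy model or a sensitivity analysis, or explains why it is left out.

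**The concern.** Balancing the arms on a factor removes that factor's contribution to the true sampling variance of the treatment difference. A linear model without the factor still counts it as residual noise, so its standard error overstates the uncertainty. If sex matters to the outcome after baseline adjustment, the ANCOVA intervals are then a little wide, the tests reject slightly less than 5% of the time under the null, and some power that was available is not used. The trial plans on 60 completers with 80% power and so has little to spare. The usual principle is to analyse by the factors used in the randomisation, and doing so here needs no new data.

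**Working it through.** **1. The plan's own figure.** Section 9.1 gives the inputs: "Assuming an average baseline dysplasia index of 22% and post-therapy 11% for subjects receiving SF", and "a simulation with 10,000 trials with a sample size of 60 subjects has yielded an 80% statistical power" at two-sided 0.05 with six biopsies per subject. I assume that placebo stays at 22%. Treating 30 × 6 = 180 biopsies per arm as independent:

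- null SE = √(2 × 0.165 × 0.835 / 180) = 0.0391
- alternative SE = √((0.22 × 0.78 + 0.11 × 0.89) / 180) = 0.0387
- power = Φ((0.11 − 1.96 × 0.0391) / 0.0387) = 80.5%

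The stated 80% reproduces. Sex plays no part in it.

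**2. Linear models (the ANCOVAs).** Let R² be the share of the baseline-adjusted residual variance that sex explains. The documents give no value, so 2%, 5% and 10% are assumptions. With exact balance on sex, the true variance of the treatment contrast is (1 − R²) times what the model without sex estimates. Its standard error is therefore too large by the factor 1/√(1 − R²). Where nominal power is 80%, the standardised effect is 1.9600 + 0.8416 = 2.8016. Then:

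- type I error, sex omitted = 2[1 − Φ(1.96/√(1 − R²))]
- power, sex omitted = Φ(0.8416/√(1 − R²))
- power, sex included = Φ(2.8016/√(1 − R²) − 1.96)

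| R² | SE too large by | Type I error, sex omitted | Power, sex omitted | Power, sex included | Points forgone |
|---|---|---|---|---|---|
| 2% | 1.0% | 4.8% | 80.2% | 80.8% | 0.5 |
| 5% | 2.6% | 4.4% | 80.6% | 82.0% | 1.4 |
| 10% | 5.4% | 3.9% | 81.2% | 84.0% | 2.7 |

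The last column is taken before rounding; the rounded entries differ by 0.6, 1.4 and 2.8.

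**3. Check by simulation.** The ANCOVA was simulated with n = 60, exact 1:1 allocation within sex, an assumed equal number of men and women, and 20,000 trials per setting. Results are given as sex omitted → sex included:

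| R² | Type I error | Power |
|---|---|---|
| 0% | 4.8% → 4.8% | 77.7% → 77.6% |
| 5% | 4.3% → 4.8% | 78.6% → 80.1% |
| 10% | 4.1% → 5.2% | 78.7% → 81.6% |

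The formula and the simulation agree. The R² = 0 row shows that including sex costs almost nothing when it is irrelevant.

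**4. Primary DI model.** The linear formula does not carry over directly to a binomial GEE. As a stand-in for the constrained GEE, a binomial GLM with baseline DI as covariate and a leverage-adjusted robust standard error was simulated with n = 60. The assumptions were a between-subject SD of 0.8 or 1.2 on the logit scale and a sex log-odds ratio from 0 to 1.5.

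- Type I error was 5.1% to 6.1% without sex and 5.2% to 6.1% with it.
- Adding sex changed power by −0.3 points (69.8% to 69.55%) to +2.5 points (71.95% to 74.45%).
- In the setting with the largest gain, type I error also rose, from 5.1% to 6.1%. Part of that gain therefore reflects a slightly small standard error.

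Power here lies below 80% because subjects are allowed to differ. That is a separate matter from this point.

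**The case against.** **The harm is conditional.** Nothing in the documents links sex to DI, histology score, Ki-67, caspase-3 or TUNEL, and the models already adjust for baseline, which may absorb much of any sex difference. This stands: the omission is certain, but its cost is not.

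**The primary test.** A reader might infer that the primary DI test is conservative and its interval too wide. The check does not support this. Type I error in the stand-in was at or slightly above 5% without sex, so the figures in the step 2 table belong to the ANCOVAs only.

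**The gain from balancing.** A reader might also infer that the power gained by balancing is thrown away. It is not. With sex omitted, power is still 80.2% to 81.2%, above the nominal 80%, so part of the gain is kept.

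**Whether sex is balanced at all.** Sections 5.2 and 6 do not mention sex, so a reader might infer that allocation was never balanced on it. Section 9 states the balancing outright and nothing contradicts it; the other two sections are silent. That gap calls for clarification but does not answer the point.

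**Dropout.** Exact balance will not survive the loss from 72 to 60. This is true but minor: simulating random loss from 36 men and 36 women (an assumed split) gave a type I error of 4.1% at R² = 10%, against 3.9% with exact balance.

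**Conclusion.** The mismatch between design and analysis is real and minor. For the ANCOVAs, leaving sex out makes the tests mildly conservative if sex is prognostic beyond baseline, at a cost of under 3 power points for R² up to 10%, and has no effect if it is not. For the primary DI analysis the expected benefit of including sex is small and not assured. In neither case is the treatment estimate biased or the false-positive rate raised by the omission, so the planned analyses remain valid.

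These sizes rest on assumed values of R² and of the sex odds ratio, near-exact balance on sex among those analysed, an equal sex split in the simulations, and a stand-in for the GEE. The case for change is that the choice is one-sided: there is almost nothing to lose and a little to gain. Prespecification also removes a later choice between adjusted and unadjusted results.

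**What to change.** - In section 9.1, add sex as a fixed covariate to the DI GEE and to the ANCOVAs for average and worst score. In section 9.2, do the same for Ki-67, caspase-3 and TUNEL. Otherwise, state why sex is omitted.
- For the GEE, specify a small-sample correction to the robust standard error. Leverage-adjusted residuals with a 1.96 critical value still gave up to 6.1% in the stand-in, so a t reference or a stronger correction is worth considering.
- State the GEE link, which section 9.1 does not give. If it is logit, say that the odds ratio is conditional on sex, or report a standardised marginal difference in DI.
- In sections 5.2 and 6, describe the balancing by sex so that they agree with section 9, including the strata and how treatment numbers are issued within them.

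The cost is one degree of freedom per model and a few sentences of text. Sex is known at randomisation, so no data collection is added.

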9.1 Statistical Analysis for histological responses

Endobronchial histology scores will be first summarized within each bronchoscopy by using 3 separate endpoint measures pre and post treatment respectively: 1) dysplasia index (DI, number of biopsies with dysplasia/total number of biopsies x 100), 2) average of all histological scores (all biopsies scores/number of biopsies), and 3) worst biopsy score. The 3 summary end points will be analyzed within 4 different biopsy site groupings: all biopsies, biopsies from the 6 standard endobronchial sites only, site-matched biopsies from both bronchoscopies, and site-matched biopsies where the baseline biopsy is non-normal. For each patient, the mean of each of endpoints separately for each of biopsy site groupings pre and post treatment are then calculated. The primary endpoint is the dysplasia index (DI), which has a binomial distribution with at least 6 “trials” (i.e., 6 predetermined biopsy sites), and will be analyzed by generalized estimating equations (GEE) that constrains average baseline DI to be the same for both treatment and placebo groups, and tests whether average follow-up DI differs between the SF treatment and placebo groups. All other endpoints and biopsy site groupings are secondary endpoints. The primary analysis for the average and worst dysplasia scores will be a linear regression that assesses the difference in post-treatment scores by the two treatment groups, controlling for the same scores at pre-treatment. This analysis of covariance (ANCOVA) approach has optimal efficiency in a study design to assess the pre- and post-treatment measures with high within-subject correlation due to repeated measures (80). No interim analyses for futility or superiority will be performed, other than ongoing safety monitoring.

Sample size consideration. In the iloprost trial, 57 former smokers were randomized to receive oral iloprost or placebo for 6 months. Treatment effects (adjusted for baseline levels) were statistically significant ($P \leq 0.01$) for all 3 endpoints (dysplasia index, average dysplasia score, worst dysplasia score). Anticipating a 20% dropout rate over 12 months, we will randomize at least 72 study subjects to ensure that 60 subjects complete our SF study. Assuming an average baseline dysplasia index of 22% and post-therapy 11% for subjects receiving SF, a simulation with 10,000 trials with a sample size of 60 subjects has yielded an 80% statistical power to detect a statistically significant (two-sided $p < 0.05$) treatment effect, using generalized linear models (binomial family, 6 biopsies) after controlling for baseline levels of DI. Calculations are similar for other endpoints, and actual power should be greater than the DI measure because they are continuous measures and have observed within-subject correlation (i.e., repeated measures).

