3. PATIENT SELECTION

Seventy-two volunteers will be recruited for this phase II clinical trial.

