Trace	22	663	2.58 (1.43-4.66)
Mild	37	493	5.04 (2.94-8.62)
Moderate/severe	16	315	3.20 (1.65-6.23)
P for trend			<0.0001

* Adjusted for age, sex, years of cigarette smoking, and number of cigarettes per day.

The presence of mild, moderate or severe radiographic emphysema on the LDCT scans at baseline was significantly associated with a 3- to 5-fold increased risk of developing lung cancer compared to smokers without emphysema (61).

We will recruit subjects for the present study from the existing PluSS participants who had mild, moderate or severe emphysema or GOLD II-IV COPD. Among the original PluSS participants who, as of 12/31/2015, were <75 years old, alive, free of cancer, and had quit smoking within the past 15 years, 356 had GOLD II-IV COPD (with or without emphysema), and additional 167 with mild, moderate or severe emphysema (without COPD). All these 523 subjects are potentially eligible for the proposed study. Based on our previous experience in the Iloprost study (22), which used a very similar protocol as the one proposed here, there was a 20% recruitment rate. Thus, we expect to fulfill our recruitment goal of at least 72 former smokers into the study within the first 3 years of the proposed study. With a 20% dropout rate based on our previous experience (22), we expect to have 60 study subjects who will complete the entire course of the trial.

If the proposed chemopreventive agent is effective, it will bring beneficial effect for study participants on reducing their risk of lung cancer. After the end of the study, all study participants can conduct their oral intake of Avmacol® since this dietary supplement is relatively cheap and commercially available.

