Sample Size Consideration. The Affymetrix Human Gene 1.0 ST Array contains ~36,000 gene transcripts. The proposed study with 30 subjects per group will have a 85% power to detect a 2-fold gene expression difference pre and post treatment ($\log_2 |d|=1.0$, $\sigma_d = 0.7$) for 23 identified cancer-related genes at a false discovery rate (FDR)<0.05 using the method of Liu and Hwang (83), assuming 99.9% non-differentially expressed genes ($\pi_0 = 0.999$). Similarly the study will have a 96% power for 280 PMLs-related genes (i.e., $\pi_0 = 0.990$), and a 99% power for 5% differentially expressed genes (i.e., $\pi_0 = 0.950$) in exploratory analysis.

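### At the plan's own 20% dropout, 72 randomised gives 57.6 completers, not 60, and the powers in 9.1, 9.2 and 9.3 all use the 60

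*Combined protocol and SAP*

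**What the plan says.** The completer count appears twice. Section 4.2 says: "With a 20% dropout rate based on our previous experience (22), we expect to have 60 study subjects". Section 9.1 says: "Anticipating a 20% dropout rate over 12 months, we will randomize at least 72 study subjects to ensure that 60 subjects complete". The number to be randomised is fixed in two other places. Section 3 says: "Seventy-two volunteers will be recruited for this phase II clinical trial". The opening of section 9 says: "The planned sample size is 72 subjects (36 per treatment arm".

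Three power statements then use 60 completers:

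- **9.1, DI (primary endpoint):** 80% power at 60 subjects, from a simulated binomial model with six biopsies and adjustment for baseline. The rates given are: "Assuming an average baseline dysplasia index of 22% and post-therapy 11% for subjects receiving SF". There is no placebo follow-up DI and no value for any within-patient correlation. The analysis planned in the same section is a GEE that holds mean baseline DI equal in the two arms.
- **9.2, Ki-67:** "we simulated 10,000 sets of data (n=60 each) and found an 84% statistical power", for a 37% reduction.
- **9.3, gene expression:** "The proposed study with 30 subjects per group will have a 85% power" for the 23-gene set. For the larger signature, "Similarly the study will have a 96% power for 280 PMLs-related genes". The power is 99% when 5% of genes are differentially expressed.

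Section 9.4 bases the adverse event comparison on all 72 subjects.

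**The concern.** The two completer statements contradict the dropout rate they quote. The likely cause is that 60 was multiplied by 1.20 instead of divided by 0.80; the first gives 72, the second 75. Because the 60 is carried into three sections, every efficacy power in the plan assumes slightly more patients than the plan expects to have. The primary power has least room, since it is stated at exactly 80%. A reader who wants to restate it also finds that two inputs to the DI simulation are missing from the text.

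**Working it through.** **Completers.** Inputs: 72 randomised, 36 per arm (section 9); dropout 20% (4.2 and 9.1).

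- Expected completers: 72 × 0.80 = 57.6, or 28.8 per arm.
- Expected dropouts: 72 × 0.20 = 14.4. Sixty completers allows only 12, and 12/72 = 16.7%.
- Needed for 60 completers: 60/0.80 = 75 (76 for equal arms).
- The plan's figure: 60 × 1.20 = 72.
- If patients drop out independently at 20%, the binomial chance that at least 60 of 72 complete is about 30%.

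**DI power.** Inputs: 22% and 11%, six biopsies, two-sided 0.05 (9.1). Assumed, because not stated: placebo stays at 22%, and a patient's biopsies are independent. With n biopsies per arm, s0 = √(2 × 0.165 × 0.835/n) and s1 = √((0.22 × 0.78 + 0.11 × 0.89)/n). Power is Φ((0.11 − 1.96 s0)/s1) with pooled variance and Φ(0.11/s1 − 1.96) with unpooled variance.

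- At 60 completers, n = 6 × 30 = 180, s0 = 0.0391, s1 = 0.0387: power 80.5% pooled, 81.1% unpooled. The stated 80% is reproduced.
- At 57.6, n = 6 × 28.8 = 172.8, s0 = 0.0399, s1 = 0.0395: power 78.9% pooled, 79.5% unpooled. The loss is about 1.6 points.
- Simulation with independent biopsies, 4,000 trials per case: the baseline-constrained GEE gave 80.3% and 81.3% at 60 (two implementations), and 78.4% and 79.6% at 58. A baseline-adjusted binomial GLM gave 79.6% at 60. Monte Carlo standard error is √(0.8 × 0.2/4,000), about 0.6 points.

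**Ki-67 power.** Inputs: log-scale variance 0.3480 (SD 0.590); effect −ln(0.63) = 0.462 for a 37% reduction, or ln(10.7/6.7) = 0.468 from the stated medians (9.2). Method: two-sample t test without baseline adjustment.

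- 30 per arm: 84.7% and 85.6%, against the stated 84%.
- 28.8 per arm: 83.2% and 84.1%. The loss is about 1.5 points.

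**Gene expression power.** Inputs: difference 1.0, SD 0.7, FDR 0.05 (9.3). By the Liu–Hwang condition, the per-gene significance level α solves α = power(α) × (0.05/0.95) × (1 − π0)/π0.

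| Set | π0 | Stated | 30 per group | 28.8 per group |
|---|---|---|---|---|
| 23 genes | 0.999 | 85% | 85.4% | 82.2% |
| 280 genes | 0.990 | 96% | 96.1% | 95.0% |
| 5% of genes | 0.950 | 99% | 99.0% | 98.6% |

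**Sensitivity of DI power to the unstated inputs.** All values below are assumptions, with no baseline adjustment. Correlation among biopsies is entered through the design effect 1 + (m − 1) × ICC, at 57.6 completers and placebo 22%.

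- Six biopsies: ICC 0.02 gives 172.8/1.10 = 157.1 effective biopsies per arm and about 75% power; ICC 0.05 gives 172.8/1.25 = 138.2 and about 70%.
- Twelve biopsies: ICC 0.02 gives 345.6/1.22 = 283.3 and about 94%; ICC 0.05 gives 345.6/1.55 = 223.0 and about 88%. Section 8.1.1 allows up to three biopsies at each of six sites, but biopsies from one site may be more alike than a single ICC allows, so these two figures may be optimistic.
- Placebo follow-up DI of 20% or 24%, with six independent biopsies: 63.8% or 89.2% (65.6% or 90.4% at 60 completers).

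**The case against.** The strongest reply is that nothing of consequence changes. The slip is 2.4 patients. The DI shift of about 1.6 points is of the same order as the spread between methods, and one simulation of the stated model type is already at 79.6% with 60 completers. For Ki-67 the direct calculation at 28.8 per arm is 83.2–84.1%, so the stated 84% is hardly disturbed, and the planned adjustment for the pre-treatment score could recover the difference. The gene expression aims are exploratory. All of this stands, and it limits the size of the point. It does not make 57.6 equal to 60. Nor does the phrase about randomising at least 72 help, because sections 3 and 9 plan 72.

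A reader might also infer more than the documents support:

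- **That the primary endpoint falls below 80% power.** Not shown. Whether the count alone takes it across 80% depends on the method. Correlation among biopsies would lower power, but no value is given; baseline adjustment, where baseline and follow-up are correlated, and more biopsies would raise it.
- **That the missing placebo DI is an error.** Placebo staying at the 22% baseline is the natural reading and reproduces the stated 80%. This is a reporting gap.
- **That a binomial GLM for power contradicts a GEE for analysis.** With independent biopsies the two agree closely. The choice matters once correlation among biopsies is assumed.
- **That a null result could not be interpreted.** It would be judged by its estimate and confidence interval, which reflect the correlation actually observed.

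**Conclusion.** The completer count is wrong as written: 72 randomised at 20% dropout gives 57.6, and 60 requires either 75 randomised or dropout of no more than 16.7%. That conclusion rests only on the plan's own figures. The powers in 9.1, 9.2 and 9.3 inherit the count; 9.4 does not. The cost is about 1.6 points for DI, 1.5 for Ki-67, 3.2 for the 23-gene set, 1.1 for the 280-gene set and 0.4 for the 5% set. The DI figure assumes placebo at 22% and six independent biopsies. The absent placebo DI and biopsy correlation are a reason to document the rerun simulation, not evidence that the trial is underpowered. It should be fixed because it is certain, repeated and cheap to correct, not because it threatens the trial.

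**What to change.** In 4.2 and 9.1, either state about 57–58 completers at 20% dropout, or keep 60 and state that it requires dropout of at most 16.7%. Make the powers in 9.1, 9.2 and 9.3 agree with whichever is chosen.

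Rerun the DI simulation at 57–58 completers using the planned baseline-constrained GEE with robust variance. State the assumed placebo follow-up DI, the correlation among a patient's biopsies and the number of biopsies per patient. As the documents give no correlation value, show the power over a plausible range.

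The cost is revised wording in four sections and one simulation, with no added patients, visits or procedures. The downside is a slightly less favourable stated power. Randomising 75 (76 for equal arms) would also restore 60 expected completers, but a loss of this size does not require it.
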